
1.1.5 PD-1 and PD-L1 in breast cancer

Inhibition of the PD-L1/PD-1 axis has been a major milestone in many cancer types. However, its relevance in breast cancer remains less clear. Expression and upregulation of PD-L1 is variable in breast cancer, and found to be high in TN and HER2+ disease. Increased PD-L1 expression has been observed in hormone therapy resistance, frequently reported with loss of the progesterone receptor (PR), a measure of hormone therapy resistance⁵. Hence, PD-1 inhibitors may have a role in hormone therapy resistant breast cancer. However, PD-1 inhibitors may be more effective after epigenetic immune priming. This proposal is focused on the potential role of epigenetic immune priming to reverse hormone therapy resistance (HTR) in pre and postmenopausal breast cancer.

Recent data suggests that PD-L1 expression is low in a majority of patients, which may confer poor response to PD-1 or PD-L1 check point inhibitors. Preclinical in vitro and in vivo studies, including ours, suggests that HDAC inhibition using vorinostat increases PD-L1 transcription

and cellular expression in breast cancer cells, including ER+ hormone sensitive and resistant as well as TN cells.

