1.3 Rationale for the Proposed Study

1.3.1 Rationale for Epigenetic Immune Priming (EIP):

Clinically, epigenetic immune regulation has been implicated in priming lung cancer cells to PD-1 inhibitors which resulted in prolonged responses^{3,4}. The efficacy of PD-1 inhibitors has not been established; however the expression of PD-L1 in ER+ breast cancer is low. PD-L1

expression however has been shown to be a poor predictor of survival and PD-L1 expression has been suggested to increase as ER+ tumors become resistant to therapy.

The role of epigenetic modulation has been studied extensively in breast cancer therapy. Several investigators have shown that HDAC inhibitors have immune modulatory functions, including modulation of Tregs, FoxP3 expression, changes in TIL expression, induction of PD-L1 expression and blockage of PD-1. We have previously shown that epigenetic modulation with an HDAC inhibitor can reverse hormone therapy resistance and force cells into programmed cell death¹. Based on these preclinical studies, we had proposed two clinical trials testing HDAC inhibitors with hormonal therapy in ER+ breast cancer.

We hypothesize that pre-exposure of breast cancer cells to the HDAC inhibitor vorinostat (i.e., Arm A, sequential treatment) will result in down regulation of T-regulatory cells (Tregs) and FoxP3, which will increase the efficacy of PD-1 inhibitors, as measured by ORR, and prime cells to increased immune response. We therefore anticipate the schedule of administration may play an important role in the administration of this combination strategy.

Recent preclinical studies have further suggested that epigenetic priming may be even more effective in ER-negative tumors that do not respond to Immune check point inhibitors or have low PD-1/PD-L1 expression. The goal of this study is to demonstrate that Vorinostat can increase PD-1 and PD-L1 expression.

1.3.1.1 Prior studies with vorinostat in breast cancer:

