3.3.1 Inclusion Criteria

1. Pre and postmenopausal women or men with stage IV ER+ breast cancer histological or cytological confirmation

ER-positive tumors

- a. Progressed after at least one line of hormonal therapy

- b. Any number of prior chemotherapy in the metastatic setting
- c. Any number of prior hormonal therapies.
- d. HER2 positive or negative

ER-negative tumors

- e. PD-L1 low, high or unknown
 - f. Progression after prior PD-1 or PD-L1 inhibitors allowed
 - g. HER2 positive or negative
2. 18 years or older.
 3. Eastern Cooperative Oncology Group (ECOG) Performance Status of ≤ 2 .
 4. Understand and voluntarily sign an informed consent prior to any study-related assessments or procedures are conducted and are able adhere to the study visit schedule and other protocol requirements.
 5. Consent to paired tumor biopsy, for accessible tumors
 6. Measureable tumor by RECIST criteria v.1.1
 7. Per Good Clinical Practice, any toxicity related to prior therapies that, in the opinion of the investigator, would potentially be worsened with anti-PD1 therapy should be resolved to less than Grade 1
 8. Adequate organ function within 14 days of study start:
 - o Absolute neutrophil count (ANC) $\geq 1.5 \times 10^9/L$
 - o Hemoglobin (Hgb) $\geq 9g/dL$ (may transfuse if clinically indicated)
 - o Platelets (plt) $\geq 100 \times 10^9/L$
 - o Potassium within normal range, or correctable with supplements;
 - o AST and ALT $\leq 2.5 \times$ Upper Limit Normal (ULN) or $\leq 5.0 \times$ ULN if liver tumor is present;
 - o Serum total bilirubin $\leq 1.5 \times$ ULN
 - o Serum creatinine $\leq 1.5 \times$ ULN, or 24-hr clearance $\geq 60ml/min$; and
 9. Females of child-bearing potential (defined as a sexually mature women who):
 - o Has not undergone a hysterectomy (the surgical removal of the uterus) or bilateral oophorectomy (the surgical removal of both ovaries) or,
 - o Has not been naturally postmenopausal for at least 24 consecutive months (i.e., has had menses at any time during the preceding 24 consecutive months).

Must have negative serum pregnancy test within 7 days before starting study treatment in females of childbearing potential (FCBP) and willingness to adhere to acceptable forms or birth control (a physician- approved contraceptive method (oral, injectable, or implantable hormonal contraceptive; tubal ligation; intra-uterine device; barrier contraceptive with spermicide; or vasectomized partner).

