To identify individual genes whose expression levels at pre-treatment are associated with pCR, we will apply two-sample *t* tests to compare responders and non-responders. Adjusted P values controlling for false discovery rate (Benjamini and Hochberg method) will be derived. In addition, to assess association of pre-specified immune gene signature with response, the median expression level of the component genes will be used to represent the signature and two-sample *t* tests will be used. For genes or signatures that emerge as significantly associated with response, logistic regression models will be used to assess their independent association with response after adjusting for known clinical prognostic factors. To identify pharmacodynamic markers, paired *t*-test will be carried out to examine immune gene expression differences between pre-treatment and post treatment samples. Additionally, association of gene expression levels after epigenetic priming with long term efficacy outcomes, such as PFS and DFS, will be explored using the Cox proportional hazards regression model. Hierarchical clustering superimposed with response status, relevant baseline or prognostic characteristics or

experimental factors will be performed using Spearman correlation and complete linkage to visualize the discriminating power of the immune gene expression and the correlative structure among the genes and the samples.

T cell receptor (TCR) deep sequencing

The change in tumor-infiltrating TCR between pre-treatment and post-epigenetic priming will be assessed by calculating the number of unique clonotypes comprising the top 25th percentile of cumulative reads after sorting by clone abundance. Repertoire change between sequencing experiments will be measured using Morisita's distance. This analysis will also be performed in subjects receiving adjuvant chemotherapy using the same statistical techniques to evaluate the impact of adjuvant MPDL3280A on circulating T cell repertoire remodeling.

Genomic signatures of response

It is hypothesized that tumors with highly mutated or copy-aberrant genomes will either overexpress native proteins or express novel mutant proteins, both of which may be recognized by the immune system and serve as tumor-specific antigens. Therefore the effect of genomic mutations on the immune landscape will be investigated in each of the cohorts in this study as follows.

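### The gene-expression screen in 8.3.4.1 uses pCR and DFS, which are not endpoints of this stage IV trial, and its t test names no ER term; if all arms are analysed together and response differs by ER status, genes that only mark ER status can be flagged.

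*Combined protocol and SAP*

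**What the plan says.** Section 8.3.4.1, under immune cell mRNA signatures, looks for genes whose "expression levels at pre-treatment are associated with pCR". The method is two-sample t "tests to compare responders and non-responders", for single genes and for pre-specified signatures. For the gene screen, "Adjusted P values controlling for false discovery rate (Benjamini and Hochberg method) will be derived"; no FDR level is given. Genes or signatures found significant then enter logistic regression "after adjusting for known clinical prognostic factors"; the factors are not listed. A Cox model relates post-priming expression to "long term efficacy outcomes, such as PFS and DFS".

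The rest of the plan describes a different setting. Section 3.3.1 enrols "Pre and postmenopausal women or men with stage IV ER+ breast cancer histological or cytological confirmation", goes on to list ER-negative tumours under the same criterion, and requires a RECIST-measurable tumour. The endpoints in 2.4.1 and 2.4.2 are 24-week response (CR, PR or SD), duration of response, PFS and OS. pCR appears nowhere else, and DFS otherwise only in the abbreviation list. The same part of 8.3.4.1 also refers to adjuvant use of MPDL3280A, which is not a study drug, so the text may have been carried over from another trial.

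**The concern.** There are two separate problems.

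**Outcome.** No scheduled resection could yield a pathological response, and patients with measurable metastatic disease are not disease-free. With pCR set aside, the plan supports two meanings of responder: SD or better at 24 weeks (8.3.2) or CR/PR (7.3). These are different groups, and the choice should be made before the expression data are seen.

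**ER status.** The t test names no arm, cohort or ER term. Its neighbours do: the PD-L1 logistic model includes study arm and the genomic analysis is by cohort (both 8.3.4.1), and flow cytometry is by arm (8.3.4.2). ER status confounds a combined screen if it is related both to expression and to response. On expression, 1.1.5 says "Expression and upregulation of PD-L1 is variable in breast cancer, and found to be high in TN and HER2+ disease" and 1.3.1 says "the expression of PD-L1 in ER+ breast cancer is low". On response, 1.3.1 suggests priming may work better in ER-negative tumours. Arm C also omits tamoxifen, and 3.3.1 lets its patients have progressed on earlier PD-1/PD-L1 inhibitors. Benjamini-Hochberg does not cure this: the marginal association is real, but it reflects tumour type and not response.

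**Working it through.** **1. The plan's own figures.** The expression text gives none. The nearest are the per-arm Simon figures in 8.2, which supply the arm size and the 10% and 30% response rates used below. With a stage 1 stop at 1 or fewer of 10, n = 29 and rejection at 6 or more (this cut-off is not stated; it is the one that reproduces the figures):

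P(reject | p) = Σ(x = 2 to 10) C(10,x) pˣ(1−p)¹⁰⁻ˣ · P[Bin(19,p) ≥ 6−x]

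This is 0.0471 at p = 0.10 and 0.8051 at p = 0.30, as stated.

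**2. Responder definition.** In the prior trial (1.3.1.1), response or SD for at least 24 weeks was 40% and objective response 19%. So (40 − 19)/40 = 0.525: about half of the broad responders are non-responders under the narrow definition.

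**3. Inputs for the ER question.** From the plan: 87 patients at most (3.2), that is 3 × 29, so 58 ER+ and 29 ER-negative. Assumed: usable tissue from all 87; a gene with SD 1, shifted by d = 1, 2 or 3 SD between ER groups and unrelated to response within each; two-sided 5% test; and the response rates by ER status shown below.

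**4. Hand calculation at 30% (ER+) against 10% (ER-negative).**
- Expected responders: 58 × 0.30 + 29 × 0.10 = 17.4 + 2.9 = 20.3; ER+ share 17.4/20.3 = 0.857.
- Expected non-responders: 40.6 + 26.1 = 66.7; ER+ share 40.6/66.7 = 0.609.
- Spurious mean difference: d × (0.857 − 0.609) = 0.248d.
- Variance within response groups: 1 + v·d², with v = (20.3 × 0.857 × 0.143 + 66.7 × 0.609 × 0.391)/87 = 0.211.
- SE = √[(1 + 0.211d²)(1/20.3 + 1/66.7)] = 0.279, 0.344, 0.432 for d = 1, 2, 3.
- z = 0.89, 1.44, 1.73; rejection ≈ Φ(z − 1.96) + Φ(−z − 1.96) = 14%, 30%, 41%.

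With equal response rates the two ER+ shares are equal, z = 0, and the rate is 5%.

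**5. Simulation (2,000 to 4,000 datasets per scenario; ranges are across runs).** False-positive rate of the unadjusted t test:

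| Response, ER+ / ER-negative | d = 1 | d = 2 | d = 3 |
|---|---|---|---|
| 30% / 10% | 13-14% | 28-30% | 40-41% |
| 40% / 10% | 23% | 51-52% | 69-70% |
| 10% / 30% | 17% | 37-38% | 49-50% |
| 30% / 20% | 7% | 10% | 13% |
| equal rates | 4-6% | 4-6% | 4-6% |

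With ER status in the model, every scenario gives 4-6%. If all three arms stop at stage 1 (20 ER+, 10 ER-negative; 30%/10%; d = 2), the rate is 10.7% unadjusted and 4.9% adjusted.

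**6. After Benjamini-Hochberg.** Assumed: 5% FDR and 1,000 genes, 200 of them ER markers. Mean number of the 200 flagged:

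| Response, ER+ / ER-negative | d = 1 | d = 2 | d = 3 |
|---|---|---|---|
| 30% / 10% | 0.1-0.2 | 2-3 | 9-12 |
| 40% / 10% | under 1 | 20-24 | about 40-50 |

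With ER in the model the mean is below 0.03. The averages hide a skew. At 30%/10% and d = 3, one run flagged 12.0 on average but flagged any gene in only 21.7% of screens, so those screens carried about 12.0/0.217 ≈ 55 ER-marker genes each. Most screens flag nothing, and a minority return a long spurious list.

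**The case against.** The strongest reply is that pooling is inferred from silence. Section 8.0 says the arms are assessed independently, and several neighbouring analyses are by arm or cohort. A reader might infer that the plan states a pooled screen; it does not. What stands is that this paragraph, unlike its neighbours, says nothing, and responders against non-responders without qualification reads most naturally as all patients.

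Second, the effect is conditional. A reader might infer that ER-marker genes will appear as response genes. That requires response to differ by ER status. The plan's hypotheses are the same in every arm (10% against 30%), and the contrasts above are assumptions.

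Third, the unadjusted rates are not the yield of the planned gene screen, which has a Benjamini-Hochberg step. They describe a single test, such as one pre-specified signature. The screen figures in step 6 are much smaller at 30% against 10%.

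Fourth, the inputs may be generous. Section 3.1 admits some patients without biopsy, 8.3.4.1 ranks assays when tissue is short, and shifts of 1 to 3 SD have no source in the documents. The cited support concerns PD-L1 alone; both ER groups admit HER2-positive tumours, and 1.1.5 and 1.3.1 say PD-L1 rises in hormone-resistant disease, which would narrow the contrast. All of this is fair.

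Fifth, ER status could be among the unlisted factors in the logistic step. It could, but that step covers only genes already selected, so the adjusted p-values of the screen stay confounded and genes masked by ER differences are not recovered.

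Finally, it is too strong to say that the plan contains no surgery: 6.2 allows it for a progressing sanctuary site, and 8.3.4.2 mentions resected tissue when available. Neither makes pCR an outcome here.

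**Conclusion.** The outcome error is certain from the text: pCR and DFS are named in an operative analysis rule and neither belongs to this trial. The practical harm is an undefined responder, with about half of the broad group changing sides in the prior trial's figures. PFS is already named beside DFS, and 8.3.2 offers a usable default, so the analysis can be rescued by wording.

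The ER point is conditional on two things: that the screen is run across all arms, and that response differs by ER status. With a 20- to 30-point difference, full accrual and large ER shifts, the inflation is material and survives multiplicity control. With a 10-point difference it is modest, and with equal rates it is absent. The analysis is exploratory, and the primary response decision in each arm is unaffected. The change should be made because the list of response genes would otherwise be hard to interpret and the correction costs almost nothing.

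**What to change.** In 8.3.4.1, under immune cell mRNA signatures:

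- Replace pCR with the 24-week response defined in 8.3.2, and give CR+PR as a sensitivity analysis.
- Replace DFS with PFS, and add OS.
- Replace the plain t test, for genes and for signatures, with a linear model of expression on response plus ER status, or stratify the comparison by ER status.
- Keep the Benjamini-Hochberg adjustment.

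The cost is wording and one degree of freedom per gene. ER status decides which arm a patient can enter, so it is already known for every patient and no new data are needed.

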2.5 Exploratory Endpoints

- To assess for post-treatment changes in TIL population, PD-L1 expression and potential indicators of response. If tumor samples demonstrate that the combination therapy converts tumors from a low (baseline) to high TIL (post-treatment) but without a corresponding increase in ORR, then we can confidently reject our hypothesis that enhancing TILs will increase pembrolizumab efficacy. Acetylation of histones in PBMCs as a response marker for vorinostat.

3 Study Design

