6.2.4.2 Histone Acetylation in peripheral blood mononuclear cells

Exposure to HDAC inhibitors results in inhibition of histone deacetylation. Histone acetylation (mainly histone H3) has been used as a biological marker of HDAC inhibitor activity. H3 acetylation has been measured successfully in PBMCs in clinical trials using vorinostat and other HDAC inhibitors. We will therefore measure H3 and H4 acetylation in peripheral blood mononuclear cells and in tumor samples of patients before and after treatment with vorinostat.

Mononuclear cells will be obtained prior to treatment initiation and repeated on day 10 (+2) and at the end of cycle 3 (day 17-19). Cells will be isolated from patient blood by centrifugation at 400 x g (Sorvall, HS4 rotor) for 30 min using a Ficoll-Paque gradient (Sigma, St. Louis, MO) as described by Sandor et al. Histone acetylation will be quantified by WB analysis of PBMCs using an acid extraction method to collect nuclear histone proteins.

6.2.4.3 Evaluation of vorinostat effects on tumor tissue acetylation and changes in estrogen receptor expression

Post-treatment tumor samples and PBMCs (as well as the vorinostat PK samples) will be obtained on cycle 3 (days 17-19) after the vorinostat morning dose. Fine needle aspirations (FNA) and core biopsies will be obtained either by an interventional radiologist (visceral disease, lymph node) or a cytopathologist (subcutaneous and skin lesions). Diff-Quick air-dry method (FNA) or touch prep analysis (core biopsies) at time of biopsy will be used to confirm the presence of tumor. Tumor samples will be divided and processed for specific techniques as listed below. An attempt for three cores will be made using the appropriate needle. Tissues will be evaluated for the effects of vorinostat on histone acetylation and estrogen expression (by IHC). For IHC, tumors will be fixed in formalin (1 hour/mm thickness), dehydrated, blocked in paraffin. Five-micron sections will be stained with the appropriate antibodies and visualized by light microscopy. Staining will be evaluated using Adobe Photoshop. As the tumor biopsies may contain a mixture of tumor and surrounding cells, cells will be stained (in addition to ER and H3) with specific antibodies used to distinguish tumor versus non-tumor tissues (e.g. cytokeratin (Keratin (5D3)) for breast cancers. PBMCs histone acetylation and ER expression will be quantified by Western blot.

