Tumor DNA will be isolated from pre-treatment tissue and from post-epigenetic priming specimens, and will be analyzed for copy number using the Human Genome CGH 244K Microarray (Agilent, Santa Clara, CA) and/or by next-generation sequencing. Results will be analyzed with DNA Analytics software (Agilent) and with the assistance of the UCSF Genome Core and the UCSF Biostatistics core. For copy number paired Wilcoxon signed-rank test will be applied to test difference of tumor gene copy number between pre and post treatment. Two-sample Wilcoxon signed-rank test will be used to test the gene copy number between tumor responders and non-responders for pre-treatment, post-treatment and changes before and after the treatment, separately. Multiple testing adjustment will be done by controlling false positive rate. Next-generation sequencing will take place using appropriate methods and biostatistical analyses. Annotation will be based on NCBI and UCSC databases. Chi-square test will be applied to obtain the significant variants associated with the clinical response.

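### The exploratory copy-number tests make no allowance for tumour-cell fraction, which the treatment is meant to alter, so they can reject when the tumour genome has not changed

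*Combined protocol and SAP*

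**What the plan says.** Under Genomic signatures of response, section 8.3.4.1 describes the material as follows: "Tumor DNA will be isolated from pre-treatment tissue and from post-epigenetic priming specimens". The specimens "will be analyzed for copy number using the Human Genome CGH 244K Microarray" and/or by sequencing. The pre/post analysis is "For copy number paired Wilcoxon signed-rank test will be applied to test difference of tumor gene copy number between pre and post treatment". A two-sample Wilcoxon test is then applied "between tumor responders and non-responders for pre-treatment, post-treatment and changes before and after the treatment, separately", with a multiplicity adjustment. On processing the section says: "Results will be analyzed with DNA Analytics software (Agilent) and with the assistance of the UCSF Genome Core and the UCSF Biostatistics core". It mentions no tumour-content estimate, minimum tumour content, microdissection or purity covariate.

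Section 6.2.4.3 recognises the issue for stained sections: "As the tumor biopsies may contain a mixture of tumor and surrounding cells", cytokeratin staining is used to tell tumour from other tissue. The check made at biopsy confirms that tumour is present, not how much of the specimen is tumour. Sections 2.3 and 2.5 look for evidence that therapy "converts tumors from a low (baseline) to high TIL (post-treatment"), and the synopsis names more tumour-infiltrating lymphocytes as the aim of priming.

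**The concern.** The stated null is that tumour gene copy number does not differ between the two biopsies. Unless the pipeline corrects for it, the array or sequencing signal is an average over tumour cells and normal diploid cells. The null actually tested is then that neither tumour copy number nor tumour-cell fraction has changed. In this trial the second part is expected to fail if the treatment works as hypothesised, because infiltrating lymphocytes carry two copies of each autosomal gene. The post-treatment biopsy is taken at the end of cycle 3, after treatment has had time to act.

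The responder comparisons on post-treatment values and on changes have a further difficulty. A shrinking lesion may contain fewer tumour cells, so response can itself alter the measurement. At stake is the interpretation of an exploratory result: a reported genomic change with therapy, or one associated with response, could partly restate infiltration or shrinkage.

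**Working it through.** **The plan's own figure.** The documents give no sample size, effect size or tumour fraction for the copy-number analysis. The only design calculation is the Simon design in section 8. There, P(reject | p) = Σ over x = 2..10 of b(x; 10, p) × P(Bin(19, p) ≥ 6 − x). The final bound of 6 or more out of 29 is not stated, but it is the one that fits. It gives 0.0471 at p = 0.10 and 0.805 at p = 0.30, matching the stated alpha of 0.0471 and power of 80.5%. The design supplies the sample sizes used below: 10 per arm at stage 1 and 29 at completion.

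**Mixture model.** With tumour fraction f and tumour-cell copies C, the measured copies are M = f·C + (1 − f)·2. Hold C fixed and let f fall from 0.6 to 0.4:

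- C = 4: M goes from 0.6×4 + 0.4×2 = 3.2 to 0.4×4 + 0.6×2 = 2.8 (log2 ratio 0.678 to 0.485).
- C = 1: M goes from 0.6×1 + 0.4×2 = 1.4 to 0.4×1 + 0.6×2 = 1.6.
- C = 2: M stays at 2.

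**Paired test.** Assumptions, none of them from the documents: baseline f has mean 60%, the SD between samples is 12 points, log2 noise has SD 0.08, and C is unchanged within each patient. The test is the two-sided signed-rank test, one gene at a time. The plan does not state an adjusted threshold, so p<0.001 stands in for one.

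| Setting (no true change) | Fall to 50% | Fall to 40% |
|---|---|---|
| n=29, 4 copies in half of tumours, nominal 5% | 25% | 69% |
| Same, p<0.001 | 2% | 15% |
| n=29, 4 copies in 70% of tumours, nominal 5% | 43% | 92% |
| n=29, 3 copies in half of tumours, nominal 5% | 17% | 48% |
| n=10, 4 copies in half of tumours, nominal 5% | 12% | 28% |
| Same, p<0.001 | 0 | 0 |

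The last row is exact: with 10 pairs the smallest two-sided p is 2/2^10 = 0.00195. With no fall in f, rejection is 4–6%. Copy-neutral genes stay at about 5%, and genes gained and lost equally often at about 5–7%.

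**Responder comparisons.** These use a rank-sum test, since the groups are independent. Assumed: 9 responders and 20 non-responders (9/29 = 31%, near the 30% target), log2 noise 0.1, within-patient change in f with SD 10 points, and f falling by 30 points in responders only. For a gain to 4 copies in 70% of tumours, nominal rejection is 5% on pre-treatment values, 32% on post-treatment values and 68% on changes. For a gain in half of tumours the last two are 9% and 37%.

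**After adjustment.** Rescale by C = 2 + (M − 2)/f. In the first example, 2 + 1.2/0.6 = 4 and 2 + 0.8/0.4 = 4, so the artefact disappears. In simulation the paired test returns to about 4–6%, even when f is known only to within an SD of 5 points. With f known, the responder comparisons on post-treatment values and changes return to about 6–7%.

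**The case against.** The strongest reply is that nominal per-gene rates are not what the plan would report, because it adjusts for multiple testing on a very large array. That has force, as the p<0.001 rows show. A Benjamini-Hochberg run over 5,000 genes, with an assumed profile in which most genes are rarely altered, gave no significant gene at n=10 or n=20, or at n=29 with a fall to 50%. With a fall to 40% at n=29, three of six runs had at least one. Adjustment does not remove the shift, however. With 4 copies in 70% of tumours and a fall to 40%, about 45% of tests still reject at p<0.001.

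Other points also stand. Twenty-nine pairs is a ceiling: genomic work comes last in the ranked tissue list, and biopsies are limited to accessible tumours. Response here includes stable disease at 24 weeks, so a 30-point fall confined to responders is an extreme case. Immune-subset quantification before and after treatment is already planned and would help interpretation, though it is not a correction. Naming core facilities, and leaving sequencing to suitable methods, might cover purity in practice, but neither specifies it and the sequencing remark does not reach the array.

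A reader might infer that the trial will report spurious copy-number changes, or might pool up to 3 × 29 = 87 patients to make the error look near certain. The documents support neither. They give no tumour fractions, and section 8.3.4.1 investigates genomic effects within each cohort.

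**Conclusion.** The gap is real but conditional. As specified, the pre/post test and the responder comparisons on post-treatment values and changes can reject with the tumour genome unchanged. This requires an actual shift in tumour fraction and a gene altered in the same direction in a fair share of tumours. Under the assumed values the inflation ranges from modest to large at nominal 5%, is much smaller at p<0.001, and is absent at that threshold with 10 patients. These rates show a range and are not a forecast.

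Treatment cannot distort the pre-treatment comparison, but baseline tumour fraction could confound it if it is related to response. It should not be assumed that the primary or secondary results are affected: the analysis is exploratory, and the design's alpha and power stand. This is a cheap improvement to consider, not a defect that threatens the trial's conclusions.

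**What to change.** Add to section 8.3.4.1, before the copy-number data are analysed:

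- Estimate tumour-cell fraction for each specimen, from the array or sequencing data or from the cytokeratin-stained sections already planned in 6.2.4.3.
- Run the paired test and all three responder comparisons, including pre-treatment, on purity-adjusted copy number.
- Set a minimum tumour content below which a specimen is non-evaluable for copy number.
- Report the change in tumour fraction beside the copy-number results.

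The cost is some bioinformatics work and the loss of a few specimens with very low tumour content. No further visits, biopsies or patients are needed.

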8.3.4.2 Immune endpoints

Immune cell activation

For each arm individually, flow cytometry of circulating immune cell subsets will also be performed on pre-treatment blood and again after 9 weeks on vorinostat (post epigenetic priming). Established flow cytometry panels will examine T cell activation. Immune cell quantification will be summarized by changes from baseline to after treatment using descriptive statistics. Furthermore, paired Wilcoxon signed-rank test will be applied to test the pre-post treatment changes. When available, immune cells digested from resected tumor tissues will also be assessed by flow cytometry.

Circulating antibody detection and characterization

Spotted antigen arrays will be used to detect circulating antibodies will be performed on sera derived from the pretreatment and after 9 weeks on vorinostat. . After standard preprocessing of the protein array data, Cluster and Treeview software will be used for unsupervised clustering of the data with Pearson correlation and complete linkage. For each array, an antigen is identified as being detected if its value is above the median. To determine the number of up- and downmodulated antibodies, the difference in log₂ intensity values of pretreatment and post-treatment samples will be taken for each patient to identify antigens that are detected

differentially due to treatment. Number of antibodies with at least 2- or 4-fold difference between pretreatment and post-treatment samples will be compared between clinical responders and nonresponders by performing two-sided Wilcoxon rank sum test.

All correlative studies and assays will be performed in the [name] lab, in conjunction with Merck, with the help of [name] and other experts in the field.

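### The copy-number comparison of responders with non-responders names a paired test (Wilcoxon signed-rank) for two unmatched groups; the rank-sum test should be named instead

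*Combined protocol and SAP*

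**What the plan says.** Section 8.3.4.1, under Genomic signatures of response, sets three comparisons of gene copy number by response status: before treatment, after treatment, and on the change between them. The test named is: "Two-sample Wilcoxon signed-rank test will be used to test the gene copy number between tumor responders and non-responders". The sentence just before it covers the within-patient question: "For copy number paired Wilcoxon signed-rank test will be applied to test difference of tumor gene copy number between pre and post treatment".

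Two neighbouring analyses handle the same distinction differently. The antibody-array counts in Section 8.3.4.2 "will be compared between clinical responders and nonresponders by performing two-sided Wilcoxon rank sum test". The mRNA analysis, also in 8.3.4.1, uses two-sample t tests for responders against non-responders and a paired t-test for pre/post change.

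The copy-number platform is the "Human Genome CGH 244K Microarray" and/or sequencing. The number of genes to be tested is not given. On multiplicity the plan says "Multiple testing adjustment will be done by controlling false positive rate", with no method or level, whereas for mRNA it says "Adjusted P values controlling for false discovery rate (Benjamini and Hochberg method) will be derived". The genomic work "will be investigated in each of the cohorts in this study", which supports an arm-by-arm reading.

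**The concern.** The signed-rank test works on differences within pairs: its null distribution comes from flipping the signs of those differences. It suits pre/post measurements in one patient. It does not suit two separate sets of patients, because no responder belongs with any particular non-responder.

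An analyst who follows the sentence literally must choose a pairing that the plan does not describe and leave out whoever is unpaired. The result would then depend on that choice, the attainable p values would be coarse, and power would be lost. All three response comparisons in the copy-number screen are affected.

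**Working it through.** **1. The plan's own figure.** The documents give no figure for the copy-number screen. The only computed figure behind the arm sizes is the Simon design in Section 8.2: stop at 0 or 1 response in 10, otherwise go to 29, testing 10% against 30%. The final cut-off is not stated. With rejection at 6 or more of 29,

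P(reject | p) = Σ over x = 2..10 of P(Bin(10, p) = x) × P(Bin(19, p) ≥ 6 − x).

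This gives 0.0471 at p = 0.10 and 0.8051 at p = 0.30, matching the stated 0.0471 and 80.5%. (Cut-offs of 5 and 7 give alpha 0.1016 and 0.0177.) So n = 29 per arm is a sound input.

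**2. Responders per arm.** Rates of 10% (null) and 30% (alternative) come from Section 8.2. The 40% rate is the clinical benefit rate of the earlier vorinostat-tamoxifen trial (Section 1.3.1.1), relevant because response here includes stable disease at 24 weeks (Section 8.3.2). The 20% rate is an intermediate assumption. In 29 patients these give about 3, 6, 9 and 12 responders.

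**3. Smallest attainable two-sided p.** Assumptions: all 29 have usable tissue, no ties, and, for signed-rank, arbitrary one-to-one pairing with k = number of responders.

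- Signed-rank: 2 / 2^k
- Rank-sum: 2 / C(29, k)

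| Responders v non-responders | Non-responders left unpaired | Signed-rank floor | Rank-sum floor |
|---|---|---|---|
| 3 v 26 | 23 of 26 (88%) | 0.25 | 5.5e-4 |
| 6 v 23 | 17 of 23 (74%) | 0.031 | 4.2e-6 |
| 9 v 20 | 11 of 20 (55%) | 0.0039 | 2.0e-7 |
| 12 v 17 | 5 of 17 (29%) | 4.9e-4 | 3.9e-8 |

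With 5 pairs the signed-rank floor is 2/32 = 0.0625, so at least 6 pairs are needed to reach 0.05.

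**4. Against a multiplicity threshold.** The number of tests is assumed.

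- Bonferroni cut-offs are 0.05/1,000 = 5e-5, 0.05/20,000 = 2.5e-6 and 0.05/244,000 = 2.05e-7. They need 16, 20 and 24 pairs. An arm of 29 allows at most 14, with a floor of 2/2^14 = 1.2e-4, so none can be met.
- Under Benjamini-Hochberg at 0.05, genes at the floor pass if their share of all genes is at least floor/0.05. With 9 pairs that is 0.0039/0.05 = 7.8% (1,563 of 20,000); with 12 pairs, about 1%.
- The rank-sum floor at 9 v 20 is below all three Bonferroni cut-offs, for 244,000 tests only just. At 6 v 23 it is below the first only, and at 3 v 26 below none.

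**5. Power for one gene.** Simulation with independent normal values, two-sided 0.05, one arbitrary pairing. Ranges show repeat runs.

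| Groups | Shift | Signed-rank | Rank-sum |
|---|---|---|---|
| 9 v 20 | 1.0 SD | 41% | 65% |
| 9 v 20 | 1.2 SD | 54–57% | 80–81% |
| 9 v 20 | 1.5 SD | 75% | 94% |
| 9 v 20 | 2.0 SD | 93% | over 99% |
| 12 v 17 | 1.2 SD | 73% | 84% |

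At 9 v 20 and 1.2 SD, two random pairings of the same data disagreed at 0.05 in about 28–30% of data sets.

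**6. Pooled arms.** With 87 patients and 26 responders the signed-rank floor is 2/2^26 = 3.0e-8, below 2.05e-7. The floor is therefore a per-arm problem.

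**The case against.** The strongest reply is that this is a slip in a name. The term two-sample, the correctly labelled paired test one sentence earlier, the matching t-test structure for mRNA and the rank-sum test for antibodies all point to rank-sum as the intent. If so, correcting the name changes no result. That stands as the likelier reading. It does not make the sentence executable: standard signed-rank software given 9 and 20 values stops with an error, and the analyst must then decide after the fact what was meant.

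Three stronger readings are tempting, and the documents do not support them.

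- A reader might infer that the plan discards most non-responders. It describes neither matching nor dropping of patients. That follows only from an assumed one-to-one pairing, and even then 29% are lost at 12 v 17.
- A reader might infer that no copy-number marker could ever be declared within an arm. That holds for Bonferroni over 1,000 or more genes. The plan does not fix the error rate, and under Benjamini-Hochberg genes could pass with 9 pairs if about 8% or more reached the floor.
- A reader might infer a general loss of more than 20 power points. The loss is about 25 points at 9 v 20 and 1.2 SD, but 19 at 1.5 SD and about 11 at 12 v 17 and 1.2 SD.

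Part of the difficulty also comes from few responders rather than from the test: at 3 v 26 the rank-sum floor is itself 5.5e-4.

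**Conclusion.** The error is in operative analysis text and is certain: a paired test is named for two independent groups, in three comparisons, with no pairing defined. Its practical effect is conditional. If the rank-sum test was meant, results are unaffected once the name is corrected. If the named test were run literally by arm, the p-value floors and power losses above would apply. They rest on 29 patients with usable tissue, no ties, one-to-one pairing and, for power, normal data. Missing biopsies or ties would raise the floors.

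Severity is minor. The analysis is exploratory, and no primary or secondary conclusion depends on it.

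**What to change.** In Section 8.3.4.1, Genomic signatures of response, name a two-sided Wilcoxon rank-sum (Mann-Whitney) test with exact p values for the comparison of responders with non-responders before treatment, after treatment and on the change. Keep the signed-rank test only for within-patient pre/post differences. This agrees with Section 8.3.4.2.

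In the same edit it would help to state the error rate, method and level for the copy-number adjustment, for example the Benjamini-Hochberg approach already used for mRNA, because the new test name does not settle that.

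The cost is one line of analysis wording, made before the data are analysed. No patient, visit, sample or assay changes.
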